4.1.3 Eligibility

Participants who meet all of the following ***inclusion criteria*** will be eligible for the study (a) female (b) age 18-45 years, (c) normal menses (22-35 day intervals) for at least 3 cycles, (d) intact uterus and cervix, (e) interested in DMPA, Nexplanon, Mirena IUD, or Copper IUD (f) willing to delay initiation of hormonal contraception for up to 1 month to complete pre-contraceptive study visits, (g) willing to use condoms or abstain from sexual intercourse for at least 24 hours before each genital tract sampling (condoms will be made available), (h) able and willing to provide informed consent, and undergo serial blood and vaginal sampling, (i) negative HIV screening.

Participants who meet any of the following ***exclusion criteria*** will not be eligible for the study: (a) pregnant within the last 3 months (b) breastfeeding, (c) history of loop electrosurgical excision procedure, conization, or cryosurgery within the past year, (d) use of hormonal contraception or IUD in the past 6 months or, (e) known history of medical condition that would interfere with the conduct of the study, (f) symptomatic vaginal infection or genital ulcer disease at screening, (g) taking medications that interact with selected contraceptive, and (h) contraindications to selected contraceptive per the CDC medical eligibility criteria(67) or judgment of clinician. For the copper IUD, exclusion criteria: allergy to copper. Participants who agree to the cervical and vaginal biopsy will have the addition exclusion criteria: allergy to lidocaine.

The cost of their selected contraceptive will be covered by research study funds. They will be informed of this during the consenting process.

4.1.4 Consent

Voluntary, informed written consent for participation will be administered prior to initiation of study activities (See Consent Forms in Appendix B). The consent form will describe the purpose of the study, the study participants' role in the study, the risks and benefits of the study, the duration of participation, the study procedures, contact persons for questions about the study (including the chair of the Institutional Review Board at Emory University and Grady Memorial Hospital), the voluntary nature of participation, and the right to decline specific questions or procedures or withdraw from the study at any time without penalty. An explanation will be provided about the use of protected health information (PHI) for research purposes and how confidentiality will be maintained as far as possible under the federal Health Insurance Portability and Accounting Act (HIPAA). Study participants will be asked to sign an authorization form for the use of PHI prior to enrollment in the study and will receive a copy for their records (Appendix B). Under no circumstances will the study participants be permitted to enroll in the study without their signed consent. All signed forms will be kept in a locked cabinet at all times.

4.1.5 Study completion

Study will be complete when 120 women, 30 in each contraceptive arm, complete the screening and the study visits. As this is a longitudinal study, we may have some loss to follow-up, and the study may be considered complete after three unanswered attempts to contact missing participants have been made. There is minimal risk, so we do not anticipate any study related adverse events or complications related to study activities that would require specific stopping rules and interim analyses.

4.1.6 Study visit schedule

Upon successful screening, participants will be scheduled for **study visit 1** three weeks

following the onset of their menses (luteal phase for women who cycle every 22-35 days). Participants will be instructed to refrain from vaginal intercourse or using intra-vaginal products for 24 hours before FGT sampling. This and subsequent study visits will occur according to the schedule outlined in [Figure 3](#) and [Table 4](#). At each visit, an interval assessment of menstruation and hormonal contraception use will be collected and used to determine the phase of the menstrual cycle. If a participant is experiencing menstrual bleeding during a follow-up visit, evaluations will be deferred for 1 week.

On the day preceding a study visit, participants will be asked to abstain from vaginal intercourse to minimize the risk of contamination of genital tract samples by semen.

Study Activities	Screen	Visit 1	Visit 2	Visit 3	Visit 4
Week from study initiation		Wk-1	WK-3	WK-15	WK-17
Week from contraceptive initiation		Pre-contraceptive		WK-12	WK-14
Informed consent	X				
Complete history & physical examination	X				
Target history & physical examination		X	X	X	X
HIV test	X	X			
Urine Pregnancy test	X	X	X	X	X
Speculum pelvic examination	X	X	X	X	X
DMPA administration			X	X	
Vulvar/vaginal biopsy			X		X
Nexplanon or Mirena or copper IUD placement			X		
**Genital sampling for study endpoints (includes 2 cytobrush samples)		X	X	X	X
***Blood sampling for study endpoints		X	X	X	X

Swab for gut microbiome		X	X	X	X
Blood testing for RPR and HSV		X			
** Cervicovaginal lavage for HIV target inflammatory/immune cells, Swab for multiplex PCR for STIs and swab for Wetprep/Nugent Score and vaginal microbiome, vaginal PH, endocervical cytobrush samples of genital specimens for immune phenotyping					
*** Blood for HIV target inflammatory/immune cells, E2 and P4					

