pg/ml) at about 4 – 6 months and remain sufficient to prevent pregnancy for 3 years. Although it initially suppresses follicular development and estradiol production, ovarian activity slowly increases after 6 months, and follicle stimulating hormone and estradiol levels are almost normal thus serum estrogen concentrations are significantly higher compared to that observed with DMPA use.(65) The **levonorgestrel releasing intrauterine device** (Mirena IUD) has a steady state plasma levonorgestrel concentration of 150-200 pg/mL that is reached in the first few weeks after placement of the IUD with levels maintained for up to 5 years after insertion. There is no change in serum estradiol and progesterone concentrations in Mirena IUD users compared to non-users; women with Mirena IUDs continue to have normal ovulatory function (66). There is a gradual reduction in endometrial thickness with the Mirena IUD with an associated gradual reduction in blood flow to spiral-arteries to the endometrium and menstrual blood flow.

Although systemic levels of Lng are low, it is unknown how the high concentrations localized to the FGT may impact local immune function. *Given the salutary effect of estrogen on the FGT, we speculate that Mirena IUD and Nexplanon, due to reduced suppression of endogenous estrogen compared with DMPA, will have lower impact on mucosal immune function and therefore be less likely to increase HIV acquisition risk.* The **copper IUD** is a non-hormonal method that provides effective contraception up to 12 years. Although the copper IUD does not impact the normal hormonal milieu, different changes in the local immune environment are potential and may impact infection risk.

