4.2 Study visits

A brief questionnaire to assess sexual behavior and bleeding or vaginal symptoms will be asked, urine will be collected for a pregnancy test, a pelvic exam will be performed with measurement of vaginal pH using a PH meter, a swab will be collected for a wet-mount, a swab for multiplex PCR of vaginal fluid, a swab for vaginal microbiome, a CVL collection (for immunological testing and prostatic specific antigen (PSA)), a swab for gut microbiome, and blood (for immunological testing and hormonal concentrations). At visit 1, additional blood will be collected for HSV serology, HIV and RPR. At visit 2 and visit 4, a cervical or vaginal biopsy will be performed for a subset of participants that consent (10 per contraceptive arm) so that one or more samples of tissue from the cervix or vagina are acquired for evaluating HIV susceptibility and inflammation markers. At visits 1-4, two [endocervical cytobrush samples](#) of genital specimens will be collected for immune phenotyping.

Hormonal contraceptives Participants will be given the option to choose between DMPA, Nexplanon, copper IUD and Mirena IUD. DMPA will be dispensed from the Grady Pharmacy Service and will be administered every 12 weeks at the standard dose of 150 mg IM, beginning from week 3 of study enrollment and repeated at week 15. A standard Nexplanon rod Implant or the IUD (Mirena or copper) will be placed at study week 3 by [name] or a trained clinician.

The cost of study contraceptives will be covered by this study.

Of note, study visits are scheduled to ensure that the collection of pre-contraceptive samples occur at both the luteal (week 1 visit) and the follicular (week 3 visit) phases of the menstrual cycle. Serum hormone levels will confirm cycle phase. Post-contraceptive samplings are strategically delayed to avoid sampling during the initial (first 3 months) phase when irregular bleeding associated use may occur. Furthermore, the proposed sampling schedule will allow us to capture data at the trough (week 15) and peak (week 17) of the concentration-time-curve for DMPA. If bleeding at the time of a scheduled visit, the visit will be postponed to occur within one week or at a subsequent point corresponding to their intended cycle phase (luteal/follicular) or drug exposure (DMPA peak or trough) of the missed visit. Because the study requires intensive and invasive sample collection, concerted efforts will be made to *enhance retention and study completion.*

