5.2 Laboratory testing

All laboratory results from assays on blood or vaginal swabs, and CVL will be documented on the laboratory results forms (Appendix E).

Specimens collected will be transported within 4 hours to the lab. Blood will be separated and immediately processed for immunophenotyping and immune cell-activation assays, as described below for the vaginal samples. The separated plasma will be aliquoted and stored at -80°C until batch testing commences, as described below for the vaginal samples. Progesterone (P4) and estrogen (E2) levels will be measured in plasma using the Milliplex kit for Luminex Assay (EMD Millipore, Billerica, MA).

A vaginal swab and anal swab will be collected and stored for future microbiome characterization via next-generation sequencing using the Ion Torrent platform to sequence 16S rDNA from bacterial species present in the vaginal compartment.

The CVL specimens will be tested for blood and leukocyte levels with a urine dipstick test and prostate specific antigen (PSA), a marker of semen exposure, using the Abacus ABACard p30 test. The sample will be centrifuged, and the cell pellet will be re-suspended in cell culture media,

Table 5: Summary of Covariates and Analytic Methods for All Specific Aims

Demographics/Behaviors: Questionnaire/Exam: Age, BMI, Race, Parity, Coital frequency

STD Screen: Vaginal swab multiplex PCR for *N.gonorrhoea*, *C. trachomatis*, *T. vaginalis*, *M. genitalium*, *T. pallidum*, HSV-1 & 2. Serum EIA for HIV & HSV. Serum RPR Kit for RPR

Candida vaginitis: Vaginal swab for KOH wet mount examination for hyphae (yeast)

Bacterial Vaginosis: Vaginal swab for gram stain assessment for Nugent score BV diagnosis

Semen: CVL supernatant ABACard® testing for qualitative prostatic specific antigen (PSA)

Serum sex hormones: Serum RIA for E2, P4

Microbiome: Next generation sequencing of 16s rDNA

and the leukocytes will be isolated from epithelial cells using Percoll gradient centrifugation. The resuspended CVL cell pellet (and PBMC pellet, separately) will be split for analysis. One half of the sample will be used for immune cell characterization (i.e., T cell subsets, HIV co-receptor expression) by antibody staining and multi-color flow cytometry using a LSR-2 platform. The other

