Data Management and Statistical Analysis: Study data will be recorded on case report forms and entered into a web-based password-protected relational database (REDCap). Repeated-measures analyses using mixed linear models will be performed with the assistance of Emory CFAR biostatistical core for study endpoints and analyzed with SAS Proc Mixed (version 9) providing separate estimates of the means by contraceptive method and time on study before (weeks 1 and 3) and after (15 and 17 weeks) contraceptive administration. An unstructured variance-covariance form among the repeated measurements will be assumed for each outcome and estimates of the standard errors of parameters will be used to perform statistical tests and construct 95% confidence intervals. The model-based means are unbiased with unbalanced and missing data,

assuming missing data are non-informative and random. Mean changes over time for each contraceptive method will be tested for linear trend. Data will be summarized using adjusted means and observed differences plus 95% confidence intervals. Statistical tests will be 2-sided. A P value ≤ 0.05 will be considered statistically significant.

For multivariable repeated-measures analyses, a mixed linear model will be fit including age, body mass index, race and parity as potential baseline confounders in addition to contraceptive method, time on study and the interaction between time on study and contraceptive method. The multivariable results will be summarized with adjusted means and 95% confidence intervals. The adjusted mean for each contraceptive subgroup (DMPA, Nexplanon, copper IUD and Mirena IUD) will be defined as the mean response obtained by fitting the statistical model at the mean age and the mean BMI of the three subgroups and averaged across levels of the other risk factors. To integrate time-dependent variables, such as BV and PSA, into the longitudinal analyses, each participant at each of the 4 scheduled visits will be classified as positive or negative for each variable. Outcome change will be compared between incident cases and the other women (baseline positive and those that remain negative) after adjusting for the other covariates.

9 Dissemination of Results

The results will be disseminated in the form of abstracts submitted to scientific meetings and manuscripts submitted to peer-reviewed journals.

REFERENCES

1. UNAIDS. UNAIDS Report on the global AIDS epidemic. 2010.

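### Fixed visits three and five weeks after menses onset cannot give one luteal and one follicular baseline across all eligible 22-35 day cycles, and section 8 has no phase variable to correct for it

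*Combined protocol and SAP*

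**What the plan says.** Criterion (c) in section 4.1.3 admits women with "normal menses (22-35 day intervals) for at least 3 cycles". Under section 4.1.6, "participants will be scheduled for study visit 1 three weeks" "following the onset of their menses (luteal phase for women who cycle every 22-35 days"). The visit table puts visit 2 at week 3, two weeks after visit 1, and the contraceptive is started at that visit. Section 4.2 gives the purpose of the two visits: "collection of pre-contraceptive samples occur at both the luteal (week 1 visit) and the follicular (week 3 visit) phases of the menstrual cycle".

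The provisions that bear on phase are:

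- A menstrual history at each visit is used to determine phase (4.1.6).
- Hormone levels are to confirm phase (4.2). They are measured in plasma, of which section 5.2 says: "The separated plasma will be aliquoted and stored at -80°C until batch testing commences".
- Bleeding is the only stated trigger for moving a visit (4.1.6, 4.2).
- Table 5 lists E2 and P4 among the covariates for all aims.
- Section 8 estimates means by method and time on study, "before (weeks 1 and 3) and after (15 and 17 weeks) contraceptive administration". The multivariable model adds age, BMI, race and parity. BV and PSA are given as examples of time-dependent variables. Neither cycle phase nor E2/P4 is named.

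For the period after initiation, section 2.1 says that "women with Mirena IUDs continue to have normal ovulatory function" and that the copper IUD leaves the hormonal milieu unchanged.

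**The concern.** Cycle length varies mainly before ovulation, so days counted forward from menses do not mark the luteal phase equally well in a 22-day and a 35-day cycle. The no-contraception baseline is the reference for every pre-to-post comparison. If it is one luteal and one follicular sample in some women and two post-ovulatory samples in others, cycle variation is mixed into the change, and the week 1 and week 3 means are not the phases they are named for in the affected women. Section 2.1 itself reports that cytokines, chemokines and antimicrobials in genital secretions vary over the cycle, which bears directly on Aim 3.

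The same question arises after initiation in the two IUD arms. Cycling is expected to continue there, while the week 15 and 17 visits are placed by DMPA trough and peak.

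**Working it through.** **The plan's own claim.** Visit 1 is luteal, and the pair gives luteal then follicular, for every eligible cycle. That is 14 of 14 whole-day lengths L from 22 to 35.

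**Inputs from the documents.** L = 22 to 35 (4.1.3). Visit 1 is 21 days after menses onset, read as cycle day 22 (4.1.6). Visit 2 is 14 days later (visit table). A bleeding visit is deferred one week (4.1.6).

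**Assumptions, not in the documents.** Luteal length 14 days; menses on cycle days 1-5; constant L within a woman.

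**Formulas.**
- Ovulation day = L − 14.
- Visit 1 is after ovulation if 22 > L − 14, that is L < 36.
- Visit 2 falls on day 22 + 14 = 36, which is cycle day 36 − L of the next cycle.
- Visit 2 is follicular if 36 − L < L − 14, that is L > 25.
- Visit 2 is in menses if 36 − L ≤ 5, that is L ≥ 31. A one-week deferral moves it to cycle day 43 − L.

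| L (days) | Ovulation day | Visit 1 (day 22), days after ovulation | Visit 2 cycle day | Visit 2 phase |
|---|---|---|---|---|
| 22 | 8 | 14 | 14 | luteal, 6 days after ovulation |
| 23 | 9 | 13 | 13 | luteal, 4 days after |
| 24 | 10 | 12 | 12 | post-ovulatory, 2 days after |
| 25 | 11 | 11 | 11 | ovulation day |
| 26-30 | 12-16 | 10-6 | 10-6 | follicular, as planned |
| 31-33 | 17-19 | 5-3 | 5-3 | menses; deferred to days 12-10, follicular |
| 34-35 | 20-21 | 2-1 | 2-1 | menses; deferred to days 9-8, follicular |

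**Count.** If any post-ovulatory day counts as luteal, 26-35 days work once the deferral is applied (10 of 14), and 22-25 miss (4 of 14). If ovulation day to +2 is not counted as luteal, 34-35 also miss because of visit 1 (6 of 14).

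**Sensitivity to luteal length (visit 1 on day 22).**

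| Luteal length | Lengths that miss, any post-ovulatory day luteal | Lengths that miss, ovulation day to +2 not luteal |
|---|---|---|
| 14 | 22-25 (4) | 22-25, 34-35 (6) |
| 13 | 22-24, 35 (4) | 22-24, 33-35 (6) |
| 12 | 22-24, 34-35 (5) | 22-24, 32-35 (7) |

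Luteal lengths of 10, 12, 13, 14, 15 and 16 days were tried with visit 1 on day 21 or day 22. A 22-day cycle fails in every case, and no case covers the whole 22-35 range.

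**After initiation, IUD arms.** Weeks 15 and 17 are 98 and 112 days after week 1, so they fall on days 22 + 98 = 120 and 22 + 112 = 134 from the index menses. With a 14-day luteal phase, constant L and no deferral:
- L = 28: cycle days 8 and 22, follicular then luteal.
- L = 31: cycle days 27 and 10, luteal then follicular.
- L = 24: cycle days 24 and 14, both luteal.

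Phase at the two post-initiation visits therefore depends on cycle length, and the schedule does not control it.

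**The case against.** The best reply is that the plan already collects what is needed. E2 and P4 are measured at all four visits, Table 5 lists them as covariates, a menstrual history determines phase at each visit, section 6.5 promises control for covariates, and the examples of time-dependent variables in section 8 are not a closed list. Much of this stands. A reader might infer that mis-phased samples would go undetected, and the documents do not support that. Batch testing prevents rescheduling, but it does not prevent classification afterwards.

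What remains is that no cut-off is given, no action follows a mismatch, and section 8 does not name phase. Because the contraceptive starts at visit 2, a missed follicular sample cannot be recovered later. Adding raw E2/P4 as covariates in all arms is not a clean substitute, since it would adjust for estrogen suppression, the mechanism the study hypothesises.

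Other limits also stand:

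- Timing is stated in weeks, so days 22 and 36 are a reading of it. Figure 3 is not shown and the operations manual is not part of the documents; either could hold visit windows.
- The schedule works for mid-range cycles, and the bleeding deferral largely repairs visit 2 in long ones.
- All four arms share the schedule, so at baseline it would bias comparisons between methods only if cycle length differs by chosen method. The documents give no information on that.

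**Conclusion.** The concern holds. Sections 4.1.3, 4.1.6 and 4.2 do not fit together: the schedule gives the stated luteal and follicular pair for about 26-30 days as planned and for 31-35 days after the bleeding deferral, with visit 1 very early luteal at 34-35. It fails at 22-25 days. The size is 4 of 14 cycle lengths, or 6 of 14 under the stricter definition of luteal (6-7 with a 12-13 day luteal phase). This rests on the assumed luteal length, visit 1 on day 22 and a stable cycle length. The failure at 22 days does not depend on which of the luteal lengths tried is used.

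Two stronger readings should be avoided. First, 4 or 6 of 14 counts cycle lengths, not women; without a cycle-length distribution the share of participants affected is unknown. Second, a reader might infer that all three aims are shown to be compromised. Section 2.1 reports variation over the cycle for secreted factors, which supports the concern for Aim 3. It describes general hormone effects on target cells but gives no cycle-phase difference for the T-cell endpoints of Aims 1 and 2. No bias in any endpoint has been estimated here.

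**What to change.** 1. **Scheduling (4.1.3, 4.1.6, 4.2).** Reconcile these sections by timing baseline sampling from each woman's usual cycle length, recorded at screening: visit 1 about 7 days before the next expected menses (cycle day L − 7), and visit 2 sampling two weeks later. Since L − 7 + 14 = L + 7, visit 2 then falls near cycle day 7 for every L from 22 to 35. A window of ±2 days would span days 5-9. With a 14-day luteal phase, ovulation is on day 8 at L = 22 and day 9 at L = 23, so the shortest cycles need a narrower window. Delete the statement that three weeks is luteal for all women. Criterion (c) does not require a fixed length, so say how a usual length is set for a woman who varies within the range.

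2. **Analysis (section 8).** Classify each pre-contraceptive sample, and each week 15 and 17 sample in the two IUD arms, as luteal or not from measured P4 with a pre-stated cut-off. Use that phase, not the nominal week, to form the baseline and to adjust the change in the IUD arms. Tie the cut-off to the assay actually used, since the text of section 5.2 names a Luminex kit and Table 5 names RIA.

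**Cost.** Visit 1 moves from day 22 to between day 15 (L = 22) and day 28 (L = 35), so by at most 7 days, and visit 2 moves with it. At L = 35 visit 2 would be on day 42, against day 43 under the present deferral. Contraception starts at visit 2, so any resulting shift in that start is for the investigators to reconcile. The analysis gains one variable. No new sample or assay is needed.

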4.2 Study visits

A brief questionnaire to assess sexual behavior and bleeding or vaginal symptoms will be asked, urine will be collected for a pregnancy test, a pelvic exam will be performed with measurement of vaginal pH using a PH meter, a swab will be collected for a wet-mount, a swab for multiplex PCR of vaginal fluid, a swab for vaginal microbiome, a CVL collection (for immunological testing and prostatic specific antigen (PSA)), a swab for gut microbiome, and blood (for immunological testing and hormonal concentrations). At visit 1, additional blood will be collected for HSV serology, HIV and RPR. At visit 2 and visit 4, a cervical or vaginal biopsy will be performed for a subset of participants that consent (10 per contraceptive arm) so that one or more samples of tissue from the cervix or vagina are acquired for evaluating HIV susceptibility and inflammation markers. At visits 1-4, two [endocervical cytobrush samples](#) of genital specimens will be collected for immune phenotyping.

Hormonal contraceptives Participants will be given the option to choose between DMPA, Nexplanon, copper IUD and Mirena IUD. DMPA will be dispensed from the Grady Pharmacy Service and will be administered every 12 weeks at the standard dose of 150 mg IM, beginning from week 3 of study enrollment and repeated at week 15. A standard Nexplanon rod Implant or the IUD (Mirena or copper) will be placed at study week 3 by [name] or a trained clinician.

The cost of study contraceptives will be covered by this study.

Of note, study visits are scheduled to ensure that the collection of pre-contraceptive samples occur at both the luteal (week 1 visit) and the follicular (week 3 visit) phases of the menstrual cycle. Serum hormone levels will confirm cycle phase. Post-contraceptive samplings are strategically delayed to avoid sampling during the initial (first 3 months) phase when irregular bleeding associated use may occur. Furthermore, the proposed sampling schedule will allow us to capture data at the trough (week 15) and peak (week 17) of the concentration-time-curve for DMPA. If bleeding at the time of a scheduled visit, the visit will be postponed to occur within one week or at a subsequent point corresponding to their intended cycle phase (luteal/follicular) or drug exposure (DMPA peak or trough) of the missed visit. Because the study requires intensive and invasive sample collection, concerted efforts will be made to *enhance retention and study completion.*

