Other actions of progesterone pertinent to HIV acquisition risk include suppression of IgG and IgA production and trans-epithelial transport within the FGT,(45-47) inhibition of CTL responses and blockade of T cell perforin expression.(48, 49) Progesterone alters the expression of cytokines, favoring Th2-type over Th1-type responses.(50) Progesterone significantly alters infiltration of genital tissue with natural killer (NK) cells, lymphocytes, and macrophages, and inhibits NK cell activity and Fc-gamma receptors (FcγR) expression on monocytes, thus reducing the functional capacity of the antibody-dependent cell cytotoxicity.(51-53) The progestin contraceptive DMPA inhibits Toll-like receptor-9-induced interferon alpha (IFN)- α production by plasmacytoid DCs thereby impairing IFN- α induced antiviral state and the innate antiviral immunity.(54) Lastly, studies have indicated that expression/secretion of chemokines, cytokines and endogenous antimicrobials in FGT secretions alter over the course of the menstrual cycle, suggesting a role for hormones in regulating their release(55, 56). For example, studies have demonstrated significant luteal phase suppression of SLPI, HBD2, HNP1-3 and lactoferrin from FGT reduced SLPI secretion in postmenopausal compared to premenopausal women(57, 58) and reduced endometrial expression of SLPI among women using DMPA(59).

Taken together, these actions of progesterone may compromise the integrity of the protective epithelial layers against HIV infection, promote enhanced homing and thus the availability of HIV susceptible cells within the FGT, and dampen the robustness of the local innate antiviral and the

adaptive secretory immune responses. As hormonal contraception can alter endogenous hormone levels and have direct impact on the FGT, well-designed studies are needed to evaluate for changes in these factors that influence HIV susceptibility following different hormonal contraceptive exposures.

Different progestin-containing contraceptives and the potential risk of HIV acquisition:
 Hormonal contraceptives employ different strategies to prevent pregnancy, including ovulation inhibition, altered endometrial structure and

Table 3: Comparative properties of three progestin-only contraceptives method

	Depot Medroxyprogesterone Acetate (DMPA)	Etonogestrel Implant	Levonorgestrel IUD
Trade-name	DepoProvera	Nexplanon	Mirena

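### Cycle phase is planned at the two baseline visits but neither scheduled nor modelled at visits 3 and 4, so in the copper and Mirena IUD arms visit-specific changes and the biopsy pairs can mix luteal and follicular samples

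*Combined protocol and SAP*

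**What the plan says.** Baseline sampling is tied to the menstrual cycle. Section 4.1.3 admits women with "normal menses (22-35 day intervals) for at least 3 cycles". Section 4.1.6 places visit 1 three weeks "following the onset of their menses (luteal phase for women who cycle every 22-35 days", and section 4.2 adds that the visits are arranged so that "the collection of pre-contraceptive samples occur at both the luteal (week 1 visit) and the follicular (week 3 visit) phases of the menstrual cycle".

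The later visits are tied to contraceptive start. The visit table in section 4.1.6 puts visits 3 and 4 at 12 and 14 weeks after initiation (study weeks 15 and 17) for all arms. Section 4.2 gives two reasons: to avoid the early months of irregular bleeding, and to "capture data at the trough (week 15) and peak (week 17) of the concentration-time-curve for DMPA".

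On biology, section 2.1 says that "women with Mirena IUDs continue to have normal ovulatory function" and that the copper IUD leaves the hormonal milieu unchanged. It also says that "secretion of chemokines, cytokines and endogenous antimicrobials in FGT secretions alter over the course of the menstrual cycle".

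On tissue, section 4.2 says: "At visit 2 and visit 4, a cervical or vaginal biopsy will be performed for a subset of participants". The subset is 10 per arm.

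On analysis, section 8 estimates a mean for each method at each time "before (weeks 1 and 3) and after (15 and 17 weeks) contraceptive administration", and tests change over time for linear trend. It names age, BMI, race and parity as baseline adjusters, and BV and PSA as examples of time-dependent variables. Cycle phase is not named. Menstrual history and serum hormones are collected at every visit, and Table 5 lists E2 and P4 under covariates, but section 8 does not say how they enter the model.

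**The concern.** The plan treats cycle phase as important enough to design around at baseline, then leaves it to chance at follow-up in the two arms where it still varies. A change from week 1 to week 15, or from week 3 to week 17, in a cycling woman may then contain a luteal-to-follicular shift, or the reverse, as well as any device effect. DMPA users, whose ovulation is suppressed, have no such phase variation after initiation. A visit-specific comparison of Mirena or copper with DMPA therefore carries a phase component on one side only. Mixed phases also add within-woman variance in arms of 30. The biopsy pair is the most exposed comparison, because tissue is taken only at visits 2 and 4 and no other visit can balance it.

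**Working it through.** **Schedule check.** Initiation is at week 3. 15 - 3 = 12 and 17 - 3 = 14 weeks, as the visit table states. Counted from visit 1, the visits fall at days 0, 14, 98 and 112.

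**Inputs from the protocol.** Visit 1 is 21 days after menses onset (section 4.1.6). Cycle length L is 22 to 35 days (section 4.1.3).

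**Assumptions not in the documents.** The luteal phase is the last 14 days of the cycle. Each woman's cycle length is constant. All 14 whole-day lengths carry equal weight. The luteal-minus-follicular difference in a marker is d, of unknown size.

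**Formula.** Cycle day = ((21 + days since visit 1) mod L) + 1. A visit is luteal (L) if its cycle day exceeds L - 14, otherwise follicular (F, including menses).

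**28-day cycle.** Days 22, 8, 8, 22, so L, F, F, L. Visit 1 to visit 3, and visit 2 to visit 4, is 98 days = 3.5 cycles.

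**All eligible lengths, no deferral:**

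| Cycle length (days) | Visits 1, 2, 3, 4 | Visits 1/3 | Visits 2/4 |
|---|---|---|---|
| 22 | L, L, L, F | same | differ |
| 23 | L, L, F, L | differ | same |
| 24 | L, L, L, L | same | same |
| 25, 26, 30-33 | L, F, L, F | same | same |
| 27-29, 34, 35 | L, F, F, L | differ | differ |

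Visits 1/3 differ at 1 + 5 = 6 of 14 lengths, visits 2/4 at 1 + 5 = 6 of 14, and both match at 1 + 6 = 7 of 14.

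**With deferral for bleeding.** Move any visit on cycle days 1-4 (assumed bleeding) by 7 days, and let visits 3 and 4 move with initiation at visit 2, as the visit table counts them. At 34 and 35 days visit 2 moves, visits 3 and 4 follow, and both pairs match. At 22 days visit 4 moves from day 2 to day 9, which is luteal. Mismatches fall to 4 of 14 for visits 1/3 (23, 27, 28, 29) and 3 of 14 for visits 2/4 (27, 28, 29). The counts are the same with bleeding on days 1-3 or 1-5. If visits 3 and 4 stayed at study weeks 15 and 17 despite a late start, the mismatches at 34 and 35 days would remain and the counts would be 6 and 5.

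**Size of the phase component, no deferral.** The number of lengths at which each visit is luteal is 14, 3, 8 and 7 for visits 1 to 4.
- Visit 1 to 3: (8 - 14)/14 = -0.43d. At 28 days: -d.
- Visit 2 to 4: (7 - 3)/14 = +0.29d. At 28 days: +d.
- Pooled: pre (14 + 3)/28 = 0.61, post (8 + 7)/28 = 0.54, shift -2/28 = -0.07d. At 28 days: 0.

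**Sensitivity, no deferral.** With a luteal phase of 12 or 14 days, within-woman cycle SD of 0, 2 or 3 days, and lengths uniform over 22-35 days, each pair mismatches in about 40-50% of women, both match in about 36-50%, and the pooled shift is -0.035d to -0.075d.

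**Biopsies.** Two arms of 10 give a ceiling of 20 of 40 pairs. At equal weights, 20 x 6/14 = about 9 pairs would be mismatched, or 20 x 3/14 = about 4 with deferral.

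**The case against.** Several points on the other side stand. Section 8 defines no pairing of visit 1 with 3 or visit 2 with 4. In a 28-day cycle each side has one luteal and one follicular visit, so the pooled contrast is unaffected. An unweighted linear trend is unaffected too: centred weeks are -8, -6, +6, +8, and the luteal visits at -8 and +8 cancel. Deferral for bleeding removes some mismatches. Section 5.1 describes the biopsy tissue as for future evaluation, and section 8 specifies no biopsy analysis. Moving only the IUD visits could make exposure time differ by method, and hormones come from stored, batch-tested plasma (section 5.2), so P4 cannot guide scheduling.

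The safeguards do not close the gap. Menstrual history and hormones record phase without timing visits 3 and 4 to it. The section 4.2 rule that moves a visit to its intended phase applies only to bleeding, and no phase is stated for visits 3 or 4. Section 4.1.6 gives a plain one-week deferral, and the two rules need reconciling. Listing E2 and P4 in Table 5 does not place phase in the model.

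A reader might infer that all 60 women in the IUD arms have mismatched pairs, or that the between-method results of Aims 1-3 are biased throughout. The documents support neither. Half the eligible lengths keep both pairs in phase even without deferral, the pooled contrast is close to balanced, and d is not given.

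**Conclusion.** The point holds in a limited form. Phase at visits 3 and 4 in the copper and Mirena arms is uncontrolled and depends on cycle length. The order reverses at 27-29 days. Over 22-35 days, each same-order pair differs in phase at 6 of 14 lengths, or at 4 (visits 1/3) and 3 (visits 2/4) with deferral. Visit-specific changes and the biopsy pairs are exposed. The pooled pre/post contrast barely is, at about -0.07d. These counts rest on a 14-day luteal phase, regular cycles, equal weight per length and, for the deferral figures, bleeding on days 1-4 with follow-up counted from actual initiation. Whether the shift matters in marker units cannot be judged, because the documents give no value for d. This is an inexpensive improvement to the plan and does not call the study's validity into question.

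**What to change.** In section 8, state that each IUD-arm visit is classified as luteal or follicular from the menstrual history and P4 already collected, by a rule fixed in advance. The P4 assay should be named, since the section 5.2 text and Table 5 give different methods. Estimate pre/post change in those arms from phase-matched visits, or include phase as a time-varying term in the cycling arms only. Do not adjust for P4 or E2 across all arms: hormone suppression is the hypothesised mechanism for DMPA, and adjustment would remove part of the effect under study.

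Report the phase of each biopsy pair, and restrict or stratify any biopsy comparison by phase match. Where visit windows allow, time IUD-arm visits 3 and 4 from reported menses in the baseline order (luteal, then follicular), without relying on P4 to schedule. Reconcile the bleeding rules in sections 4.1.6 and 4.2, and say whether visits 3 and 4 have an intended phase.

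The cost is a little more analysis work and fewer usable pairs where phase cannot be matched. No visit or sample is added.
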